If a physician committee member determines that they are no longer able to serve on the MC, the other committee members will be asked for recommendations for a replacement member, in consultation with PI. A replacement member will be identified, and the approval of NINDS will be sought prior to confirming the replacement.

In the event that the patient advocate representative makes the decision to step down, the board of the Glut1 Deficiency Foundation will be consulted, and a request for a replacement member will be made. The approval of NINDS will be sought prior to confirming the replacement of this committee member.

9.5. Data Analyses

Summary descriptive statistics: For normally distributed, continuous data, means and standard deviations will be used to describe the demographic and clinical characteristics of the patient population participating in the study and medians and semi-interquartile ranges will be used to describe characteristics of the patient population when the data are continuous, non-normally distributed. For categorical or dichotomous variables, the frequency or the proportion will be reported.

Primary Aim: The primary aim is demonstrating the benefit of C7, as measured by a change in performance on the primary attention measure for each age group. The proportion of subjects who achieved favorable outcome will be estimated along with the corresponding 95% confidence interval using an exact binomial method. We will also investigate if there will be significant differences in the proportions of favorable outcomes among three age groups using Fisher's exact test. We will make every effort to minimize the missing data. We expect minimal amount of missing data. If missing data occurs, missing data will be imputed using multiple imputation techniques.

Generalized estimating equation (GEE) analysis will be used to examine if C7 positively affects other neuropsychological (e.g., IQ, language, processing speed) and neurological performance, such as ataxia over time (baseline, 6 months, and 9 months).

Secondary Aim: A secondary aim is to evaluate the effect of C7 supplementation of a regular diet on an EEG activity and to evaluate the safety of C7 supplementation. EEG will be analyzed in 3 ways (spike-wave duration, total number of seizures and background of the EEG as described above). GEE analysis will be used to examine if there are significant changes in EEG activity and safety over time. GEE analysis will be also conducted to investigate whether attention neuropsychological scores correlate with the EEG findings.

Study end. Statistical analyses at the end of the study will examine the initial measures at baseline, 6 months, and 9 months. Repeated measurement data will be analyzed using the generalized estimating equation (GEE) approach. The GEE method has been widely used for the analysis of repeated measurement data because of its robustness to random missing and misspecification of the true correlation structure.

SAS V9.4 (SAS Institute, Inc. SAS V9.4, Cary, NC, 2014) will be used to analyze the data.

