 - 5.3.4.1. No change in type of drug treatment is the planned study conduct. It is likely that this plan will be followed by all subjects because, in clinical practice, the withdrawal of an antiseizure drug on a given patient is usually evaluated only at 2-year intervals, which exceeds the duration of this Protocol. Modest (10-25% dose) changes will be allowed per standard clinical practice in rapidly growing (young) children, whose weight normally increases on a monthly basis. These children will thus continue to be treated per standard pediatric neurological practice.
 - 5.3.4.2. Addition of a new antiseizure drug. This will be prompted by increased seizures and is equivalent to C7 failure.

5.3.4.3. Discontinuation of an antiseizure drug. This will be prompted by drug adverse events and recorded as such (as outlined below). Such events are very unlikely in patients who have been receiving a stable drug regimen (see Exclusion Criteria).

5.4. Adherence Assessment: The coordinator will call subjects and families once a month to determine adherence (by self-report), remind subjects to go in for the month two lab draw if not already done, and assess amount of oil remaining, and will prompt and procure an answer to any questions that the family may have. If any subjects are having trouble as reported during a call, [name] or M.D. co-investigator will be notified and a written plan of action will be developed. Additionally, a nutritional consult will be completed to determine if the C7 dose is still correct. If the subject's caloric intake has changed significantly enough to require a change in the amount of C7 needed, the dietician will consult with PI or M.D. co-investigator, who will contact the family to provide directions for the dose change.

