6.2.3. Intervention Discontinuation Evaluations

Subjects will return for a discontinuation visit at 6 months after initiation of treatment. Subjects undergo the same set of evaluations completed at enrollment. Subjects will complete a medical history, clinical visit, physical exam, pregnancy test if appropriate, and neuropsychological testing on the first day of the visit. Subjects will undergo a 24 hour inpatient stay with continuous EEG to capture EEG recordings in all states: non-fasting/on oil; fasting/on oil; fasting/off oil; and fasting/on oil. On day 1 or day two, subjects can have blood drawn to evaluate hematology, chemistry, and lipid panel. We will also obtain 3 mL of blood that is left over from the samples above (if available) or draw an additional 3 mL of blood to measure C7 ketones. The collection of this blood for measurement of ketones is optional. Subjects will be administered a final dose of oil on the morning of Day 2 for the purposes of fasting, on oil EEG. At that point, they will be discontinued from the oil and discharged from the inpatient stay.

If subjects wish to discontinue the oil before 6 months, we will ask them to return for a discontinuation visit as soon as feasible and remain on the oil until they return. If subjects wish to discontinue due to intolerable side effects, they will be permitted to do so, and asked to return for a final visit as soon as feasible. Many of our patients come

from out of town, and it could potentially be a matter of weeks to a month before a return visit is possible. Subjects will complete a medical history, clinical visit, physical exam, pregnancy test, and neuropsychological testing on the first day of the exit visit. On day one or day two, subjects will complete a fasting blood drawn to evaluate hematology, chemistry, lipid panel, and specialized metabolites. We will also obtain 3 mL of blood that is left over from the samples above (if available) or draw an additional 3 mL of blood to measure C7 ketones. The collection of this blood for measurement of ketones is optional. Subjects will also have a fasting EEG, and will be discontinued from the study at this visit.

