8. CRITERIA FOR INTERVENTION DISCONTINUATION

Triheptanoin supplementation will be discontinued if any of the following occur:

- Any of the cited or other adverse experiences become intolerable to the subject
- Metabolic syndrome develops as assessed by glucose and lipid profiles
- Any elevation above laboratory normal range in hepatic transaminases or creatinine is noted
- Any clinically relevant blood cell count abnormality develops
- Non-compliance occurs
- Severe intercurrent illnesses take place

Subjects who discontinue due to the above reasons will be asked to return for a final research visit to complete exit procedures and receive referrals for ongoing care if necessary. Subjects who are discontinued due to adverse events will be followed via daily, alternate-day or weekly phone calls to assess resolution of the adverse event.

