9. STATISTICAL CONSIDERATIONS

9.1. General Design Issues

In the proposed single-arm phase II trial, we define favorable impact on the neurocognitive outcome as at least 0.5 standard deviation (SD) improvement in performance on attention measures (measured as described above) after administration of C7. That is, impact on the outcome is determined by whether a treatment causes at least 0.5 SD improvement on the primary attention measure for that age group in a single arm trial and the interest is **primarily focused on reaching a decision on whether to progress with C7 to a future larger trial**. (Note: The SD is a normative parameter provided with the testing instruments). The evidence to make this decision is evaluated by testing the null hypothesis that the true efficacy rate is less than or equal to some pre-specified value. It is desirable to achieve this goal whilst minimizing the number of subjects exposed to a novel agent. Here, we use the Simon's optimal two-stage design that yields the smallest expected sample size when the null hypothesis is true.

We apply Simon's optimal two-stage design (24) using as primary outcome attention performance for each of three age groups. At least 0.5 SD improvement in performance on the primary attention measure after the administration of C7 is considered a favorable outcome. The measurement of 0.5 SD improvement is commonly accepted as the cutoff for a minimally clinically important difference, as described in various studies (e.g., 32, 33).

This protocol will yield data that allow a clear **go/ no-go decision** regarding whether C7 should proceed to an efficacy trial:

- If a favorable outcome occurs in less than 50% of subjects, we will recommend that C7 not proceed to an efficacy trial.
- If a favorable outcome occurs in at least 80% of subjects, we will recommend that C7 proceed to an efficacy trial.

The sample size estimation for this optimal two-stage design is given in Section 9.3.

If an intermediate number of subjects (51 – 79%) exhibit a favorable primary attention outcome, the rest of outcomes, including the long-term, 6-month responses, will be considered for the go/ no-go decision on the basis of impact on these outcomes and the disease process, in addition to tolerability and safety indicators.

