9.3. Sample Size and Accrual

We estimated the sample size using the primary outcome (attention) for each of three age groups. The same method will be applied for sample size estimation in each of three age groups. An improvement of 0.5 SD or more on the primary attention measure

after the administration of C7 is considered a favorable outcome. This study will yield data that allow a clear go/no-go decision regarding whether C7 should proceed to an efficacy trial: If a favorable outcome occurs in less than 50% of subjects, we will recommend that C7 not proceed to an efficacy trial. If a favorable outcome occurs in at least 80% of subjects, we will recommend that C7 proceed to an efficacy trial.

The sample size was estimated using Simon's optimal two-stage design (24). The null hypothesis that the proportion of favorable outcome is 50% will be tested against a one-sided alternative hypothesis that the proportion of favorable outcome is 80%. In the first stage, 7 subjects will be accrued. If there are 4 or fewer favorable outcomes in these 7 subjects, the study will be stopped, and we will recommend that C7 not proceed to an efficacy trial. Otherwise, 6 additional subjects will be accrued for a total of 13 subjects. If 8 or fewer favorable outcomes are observed in 13 subjects by the end of stage two, then no further investigation of C7 is warranted. This design yields a type I error rate of 0.1 and power of 80% when the true favorable outcome occurs in 80% of subjects. We plan to recruit 15 subjects with an expected 15% dropout rate resulting in 13 subjects for each age group. That is, we will recruit a total of 45 subjects for this protocol.

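### A subject the protocol calls a C7 failure can count as favorable, and no rule turns imputed outcomes into the whole-subject counts the Simon boundaries need

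*Combined protocol and SAP*

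**What the plan says.** - **Outcome.** Section 9.1: "At least 0.5 SD improvement in performance on the primary attention measure after the administration of C7 is considered a favorable outcome". Sections 9.2.1 and 9.3 use the same test-score definition and nothing else.
- **Added drug.** Section 5.3.4.2: "Addition of a new antiseizure drug. This will be prompted by increased seizures and is equivalent to C7 failure". Section 5.3.4.1 expects that probably no subject will change drugs.
- **Leaving the study.** The stopping list in Section 8 does not name an added antiseizure drug. Section 6.2.2.2 says only that exit is to be considered if clinical seizures increase significantly, with C7 stopped if a new EEG is judged clearly worse.
- **Numbers.** Section 9.3 stops at 4 or fewer of 7. The final no-go condition is "If 8 or fewer favorable outcomes are observed in 13 subjects by the end of stage two". On recruitment: "We plan to recruit 15 subjects with an expected 15% dropout rate resulting in 13 subjects for each age group".
- **Analysis.** Section 9.5, under the primary aim: "The proportion of subjects who achieved favorable outcome will be estimated along with the corresponding 95% confidence interval using an exact binomial method". The same paragraph adds: "If missing data occurs, missing data will be imputed using multiple imputation techniques".
- **Early stoppers.** Section 8: "Subjects who discontinue due to the above reasons will be asked to return for a final research visit to complete exit procedures". Section 6.2.3: "If subjects wish to discontinue the oil before 6 months, we will ask them to return for a discontinuation visit as soon as feasible". Neither section, nor 9.5, says whether that exit score enters the primary count.

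The text between 9.3 and the committee-membership paragraphs that precede 9.5 was not available, so this point rests on the rest of Section 9.

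**The concern.** There are two gaps, and both act on the go/no-go count.

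First, no text carries the failure label of 5.3.4.2 into the outcome. A subject who adds a drug because seizures increased is not required to leave. That subject can reach the 6-month test, gain 0.5 SD (possibly helped by the new drug) and be counted as favorable.

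Second, subjects with no score have no stated place in the count. Some stops are plainly treatment-related: dose intolerance (5.1.1, 5.3.3), and transaminase or creatinine elevation (Section 8). Imputation without an exception gives such subjects a chance of being favorable based on those who stayed. The result is an average over data sets, whereas the boundaries and the exact binomial interval take whole subjects. With 13 subjects per age group, one subject can decide the outcome, so the choice of rule could be made after the data are seen.

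**Working it through.** **1. Reproduce the plan (9.3).** The inputs are a 50% null, an 80% alternative, stop at 4 or fewer of 7, and pass at 9 or more of 13.

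P(pass | p) = Σ over x = 5, 6, 7 of P(X1 = x of 7) × P(X2 ≥ 9 − x of 6).

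At p = 0.50: (21×22 + 7×42 + 1×57) / (128×64) = 813/8192 = 0.099. At p = 0.80 the same formula gives 0.818. The stage 1 stop probability at 0.50 is 99/128 = 0.773. The stated 0.1 and 80% are confirmed, but they hold only for 7 and 13 fully observed binary outcomes.

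**2. A boundary example under imputation.** Suppose stage 1 was passed, 8 of 12 scored subjects are favorable, and one is imputed at the scored rate of 8/12. The pooled count is 8 + 8/12 = 8.67 of 13. In 8/12 = two thirds of data sets the count is 9 (pass). In one third it is 8 (stop). At stage 1, 4 of 6 scored plus one imputed gives 4 + 4/6 = 4.67 of 7, with the same split.

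**3. Treatment-related stoppers removed and replaced.** Assumptions, none fixed by the documents:
- the 50% null covers all treated subjects, with stoppers not favorable;
- the 6-month score decides;
- exit scores are not used;
- a fraction d of subjects stop for treatment-related reasons and are replaced by completers.

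The completer rate is then q = 0.5/(1 − d), which goes into the formula of step 1. The plan expects 15 − 13 = 2 losses per group. How many are treatment-related is not given, so d is shown over its range.

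| d | q | P(pass) | stage 1 stop | P(≥ 11 of 13) |
|---|---|---|---|---|
| 0 | 0.500 | 0.099 | 0.773 | 0.011 |
| 1/15 | 0.536 | 0.150 | 0.711 | 0.021 |
| 2/15 | 0.577 | 0.225 | 0.629 | 0.041 |
| 0.15 | 0.588 | 0.250 | 0.605 | 0.049 |

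The last column is the automatic go rule of 9.1, since 80% of 13 is 10.4, hence 11.

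**4. The same loss under pooled imputation.** Take q = 0.536 and one stage 1 subject imputed at the scored rate.
- If the pooled count need only exceed the boundary, passing takes 4 or more of 6 scored (4.67 > 4) and 8 or more of 12 (8.67 > 8): error 0.220.
- If it must reach the next whole number, passing takes 5 or more of 6 (5.83 ≥ 5) and 9 or more of 12 (9.75 ≥ 9): error 0.068.

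The error can therefore fall below or rise above 0.099, depending on a rule that is not written.

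**5. If imputation restores all 15.** No boundary exists for 15. Keeping 4/7 at stage 1, a final boundary of 8 gives error 0.159 and power 0.849, 9 gives 0.101 and 0.832, and 10 gives 0.049 and 0.773.

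**6. Added drug only.** For scale, assume that 1 in 13 adds a drug and gains 0.5 SD with probability 0.25 to 0.5, and that the null treats such subjects as failures. The scored rate is 0.5 + (1/13)×0.25 = 0.519 to 0.5 + (1/13)×0.5 = 0.538, and the error is 0.12 to 0.15. If nobody adds a drug, as 5.3.4.1 expects, the effect is zero.

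**The case against.** - **The recruitment step is not an analysis rule.** A reader might infer that 9.3 and 9.5 contradict each other on dropouts. That is too strong. The step from 15 to 13 is an allowance that implies removal without stating it, and 9.5 speaks of missing data, not dropouts. What stands is that no analysis set is named.
- **Imputation is not incompatible with the design.** Each imputed data set has a whole count. What is missing is the combining rule, and the exact interval has the same gap.
- **The deciding visit is open.** Section 9.1 sets the 6-month responses among the other outcomes, and attention is also tested on oil on Day 2 of Visit 1. Section 9.2.1 names both the acute and the long term. If Day 2 decides, a drug added in months 1 to 5 cannot matter and dropout matters little. This is fair, and it makes naming the visit the first repair.
- **The null may concern only the 13 who remain.** Then removal leaves the error at 0.099. The documents do not say which population is meant.
- **Failure in 5.3.4.2 may be a clinical label.** Sections 2.1 and 9.1 separate attention from seizure control. That is possible, but the plan should then say that the label has no bearing on the count.
- **The decision has a buffer.** Passing with 9 or 10 of 13 (69% or 77%) falls in the intermediate zone of 9.1, where tolerability and safety are weighed. This stands for the final decision. It does not cover the stage 1 stop, which 9.3 makes automatic.

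**Conclusion.** The concern holds as a gap in the primary counting rules. Followed as written, the plan can count a subject it calls a C7 failure as a success, and near a boundary the same data can mean stop or continue.

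The size is conditional. With removal and replacement, an all-treated null, a 6-month decision and no use of exit scores, the per-group error is 0.150 or 0.225 instead of 0.099, and the stage 1 stop probability falls from 0.77 to 0.71 or 0.63. A reader might infer that imputation itself raises the error to those values. The documents do not support that: under pooled imputation the figure is about 0.07 to 0.22 for one imputed subject, and its direction depends on the combining rule. Nor do they show that the trial's error is inflated as such, because neither the null population nor the deciding visit is fixed. The automatic 80% go error stays below 0.05 throughout, and the added-drug effect may be zero.

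This should be fixed before outcomes are examined; confidence is medium.

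**What to change.** Analysis wording only, in 9.2.1, 9.3 and 9.5:
1. Name the visit whose attention score decides.
2. Reconcile the favorable-outcome definition with 5.3.4.2, so that a subject who adds an antiseizure drug before that visit is not counted as favorable.
3. For the Simon go/no-go count, use whole subjects. Count those who stop before that visit for treatment-related reasons as not favorable, with the reason classified without knowledge of the attention score. Keep multiple imputation and exit-visit scores as sensitivity analyses.
4. State that the 50% and 80% rates are read under this rule, and restate error and power.

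No clinical rule for stopping or adding treatment changes. No visit or test is added, because exit testing is already planned. The extra work is the blinded classification of stop reasons.

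The cost is that attention becomes a composite endpoint. Under an all-treated 50% null the error stays at 0.099. But if 80% holds only among completers, the favorable rate is 0.8(1 − d), and power at the same boundaries falls from 0.82 to 0.75 (a quarter of the 15% treatment-related, d = 0.0375), 0.66 (half, d = 0.075), 0.53 (d = 2/15) or 0.49 (all, d = 0.15). The 80% alternative must therefore be justified as including stoppers, or the design revisited.

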6.2.2.2. Months 1-5

Each month between Visit 1 and 2, the research coordinator will contact each family to evaluate adherence and tolerability. Additionally, at month two each subject will complete safety blood work at a local CLIA-certified clinical laboratory and have the

results returned to PI at UT Southwestern Medical Center. Every effort will be made to ensure adherence to the protocol: Subjects who do not comply with the month two blood draw (i.e., those who submit blood work results 10 days or later past the due date) will receive extra guidance via telephone and secure email. The maximum tolerable period for result submission delay is 30 days, after which subjects will be evaluated for termination or, if extenuating circumstances have occurred, may have the delivery of oil delayed until they return to compliance with the protocol. Subjects determined to exhibit greater propensity to delays in the opinion of the research team will receive pre-emptive anticipatory guidance before each blood draw due date and help with local phlebotomy scheduling.

Contingency plans for any pro-epileptogenic effects of C7: This is extremely unlikely since C7 is fully consumed in the TCA cycle as a metabolic fuel source and experience with C7 has failed to show any adverse events, including epilepsy. The EEG in G1D shows preprandial spike-waves in the majority of patients regarding of apparent clinical seizure control, thus providing an individual baseline. To address the potential circumstance that C7 may be associated or coincide with a significant increase in clinical seizure frequency between visits, study exit will be considered. An additional optional procedure will include the performance of a routine outpatient clinical EEG. This procedure will be obtained and reported locally (i.e., in the area of patient residence) in an accredited clinical facility and the report forwarded to the M.D. investigators for the following decisions and interventions after clinical comparison with previous patient EEGs. If the new EEG is deemed significantly more abnormal following clinical neurophysiological evaluation by a board-certified pediatric epileptologist, C7 cessation will be followed by study exit procedures.

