9.2.2.3. Safety

C7 supplementation is safe when used over the long term (6 months) period. Subjects will experience no clinically significant changes in standard laboratory measures (blood cell count, blood electrolytes, AST, ALT, blood urea nitrogen, creatinine, lipid panel, plasma glucose and beta-hydroxybutyric acid.) and exhibit no evidence of toxicity as measured by the VA Toxicity Scale.

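### Section 9.5 tests safety with GEE at baseline, 6 and 9 months, which does not estimate the stated criterion of no clinically significant laboratory change and leaves month-2, exit and lab-triggered-stop data without a defined role

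*Combined protocol and SAP*

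**What the plan says.** The safety outcome in 9.2.2.3 is a statement about subjects: "Subjects will experience no clinically significant changes in standard laboratory measures", together with no toxicity on the VA scale. The Synopsis and Section 1.2 use the same laboratory criterion. No threshold for a clinically significant change is given.

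The only analysis named for it, in 9.5, is: "GEE analysis will be used to examine if there are significant changes in EEG activity and safety over time". No response scale, link, margin or confidence interval is given for safety. The closing paragraph of 9.5 sets the times: "Statistical analyses at the end of the study will examine the initial measures at baseline, 6 months, and 9 months".

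Three other sections bear on which values reach that analysis:

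- Section 6.2.2.2 schedules an on-oil draw between the start of C7 and month 6: "at month two each subject will complete safety blood work at a local CLIA-certified clinical laboratory".
- Section 8 stops C7 on several grounds, among them: "Any elevation above laboratory normal range in hepatic transaminases or creatinine is noted". On exit it adds: "Subjects who discontinue due to the above reasons will be asked to return for a final research visit".
- Section 6.2.3 says of the early-exit visit that "subjects will complete a fasting blood drawn to evaluate hematology, chemistry, lipid panel, and specialized metabolites", and that subjects "will be discontinued from the study at this visit".

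**The concern.** The criterion and the analysis answer different questions. The criterion asks whether any treated subject had a laboratory change that matters clinically. The analysis asks whether a set of repeated values moves significantly over time. A few marked individual changes can sit inside a non-significant group result.

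The listed times make this worse. Month 9 is three months after the oil has stopped, so month 6 is the only listed time on treatment. A subject whose month-2 value leads to a stop leaves the study at the exit visit and has no scheduled 6- or 9-month record. Values are then missing because of the safety outcome itself, and the value that caused the stop falls at no listed time. Section 9.5 justifies GEE by its robustness to random missingness, which is not this mechanism.

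Long-term safety is a secondary objective, and Section 9.1 gives supply of six-month safety data as a reason for the treatment period. Safety indicators also enter the go/no-go decision, but only when 51-79% of subjects respond.

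**Working it through.** **The plan's own figure.** No figure is stated for the safety analysis. Section 9.3 fixes the numbers available: 3 × 15 = 45 recruited, 3 × 13 = 39 expected after dropout.

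**Which values have a place in 9.5**

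| Laboratory value | On oil? | Listed time in 9.5? |
|---|---|---|
| Baseline | no | yes |
| Month 2 | yes | no |
| Early-exit visit | depends on the stop | no |
| Month 6 | yes | yes, if still in the study |
| Month 9 | no | yes, if still in the study |

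A month-2 abnormality followed by a stop therefore has no listed post-baseline time. That holds whether GEE is fitted to continuous values or to a binary abnormal/normal response.

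**Illustration of sensitivity.** Assumptions, none of them in the documents: one analyte with SD 1, within-subject correlation 0.6, n = 45, k subjects shifted upward by s SD at month 6, the others unchanged, and a two-sided 5% robust-variance z-test of mean change standing in for the GEE time contrast.

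- Variance of a change without a shift: 2 × (1 − 0.6) = 0.8, so SD = 0.894.
- For k = 3, s = 4: mean change = 3 × 4/45 = 0.267. Variance across subjects = 0.8 + (3/45)(42/45)(16) = 1.796, SD 1.340, SE = 1.340/√45 = 0.200. The mean must exceed about 1.96 × 0.200 = 0.392. With the affected subjects fixed, the mean varies with SE 0.894/√45 = 0.133, so rejection is roughly P(Z > (0.392 − 0.267)/0.133) = P(Z > 0.94), about 17%. Simulation gives about 19%.
- For k = 6, s = 4: mean change = 0.533. Variance = 0.8 + (6/45)(39/45)(16) = 2.649, SE = 0.243, threshold 0.476. Rejection is roughly P(Z > (0.476 − 0.533)/0.133) = P(Z > −0.43), about 67%. Simulation agrees.

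Simulated rejection rates:

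| Affected subjects | Shift | Values included | Post-baseline values absent |
|---|---|---|---|
| 3 of 45 | 2 SD | about 12% | about 6% |
| 3 of 45 | 3 SD | about 16% | about 6% |
| 3 of 45 | 4 SD | about 19% | about 6% |
| 6 of 45 | 4 SD | about 67% | about 6% |

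The 6% is the false-positive rate of the z-test at this sample size. With a t-test, 3 subjects at 4 SD give about 16% included and 5% absent.

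**What an incidence summary would give** (exact Clopper-Pearson limits):

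- 3/45 = 6.7%, 95% CI 1.4% to 18.3%.
- 0/45: upper two-sided 95% limit = 1 − 0.025^(1/45) = 7.9%; one-sided = 1 − 0.05^(1/45) = 6.4%.
- 0/15 in one age group: upper two-sided 95% limit = 1 − 0.025^(1/15) = 21.8%.

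**The case against.** Several stronger readings are tempting, and the documents do not support them.

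- *That the plan tests mean change.* Section 9.5 gives no response scale or link. GEE could model a binary abnormality, and the VA toxicity score is a repeated measure that suits GEE. The illustration covers the continuous case only.
- *That stopped subjects are excluded.* They are not. They are asked to an exit visit with labs, GEE accepts incomplete records, and Section 10.4.3 classes a test finding that leads to discontinuation as an adverse effect, so it is recorded. The 6% figures apply only if post-baseline values do not enter the analysis. What the plan lacks is a rule for these data.
- *That month-2 labs are excluded.* The GEE safety sentence names no times. The list comes from the study-end paragraph, and month-2 results can still lead to stopping or adverse-effect recording.
- *That non-significance will be taken as safety.* No section says so. It is a risk of interpretation.
- *That GEE should be dropped.* Section 2.2 names lipids as a possible change. Under the same assumptions a 0.5 SD shift in all 45 subjects would be detected about 96% of the time, while few subjects might cross an individual threshold.

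The monitoring-committee text before 9.5 was only partly available for this review, so nothing is concluded about safety monitoring rules.

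These points narrow the concern. They do not remove it: 9.5 still has no summary that matches the safety criterion, and no stated place for the month-2 and exit values.

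**Conclusion.** The point holds as a mismatch and a gap in 9.5. The named analysis does not estimate the stated safety criterion, its listed times contain one on-oil value, and losses at months 6 and 9 depend on the outcome under study. A subject with a month-2 abnormality who is then stopped could go uncounted if the listed times are followed, even with a binary GEE.

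The mismatch and the time points are read directly from the text. The size is illustrative. With three affected subjects, rejection is about 12-19% if they are included and about 6% if their later values are absent. Detection rises quickly with more affected subjects, to about 67% with six at 4 SD. The number affected, the shift and the correlation are all assumed. The change is worth making before analysis. It does not touch the primary outcome.

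**What to change.** In 9.5:

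1. Add as the main safety summary, for each analyte and overall, the number and percentage of all treated subjects with at least one clinically significant change at any post-start on-treatment, unscheduled or exit draw, including months 2 and 6, with an exact 95% CI.
2. Have the sponsor fix the criterion for a clinically significant change before analysis.
3. Report Section 8 discontinuations in the same form.
4. Keep GEE on continuous values as support for group-wide shifts such as lipids, with month-2 and exit values included.
5. Show the 9-month off-oil values separately.

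The cost is small: SAP wording, agreement on the criterion and one table. The scheduled draws already supply the data. The change does not add precision: the 7.9% upper limit after 0/45 comes from the sample size and should be shown with the result.
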